2. Chronic AT1 receptor blockade in subjects with compensated CHF and renal dysfunction will improve humoral function with suppression of the aldosterone and increase renal cGMP generation as compared to placebo.
3. Chronic AT1 receptor blockade in subjects with compensated CHF and renal dysfunction will improve left ventricular systolic and diastolic function and filling pressures as compared to placebo as evident by:
 - Improvement in ejection fraction

- Decrease in filling pressures with a decrease in the ratio of early mitral diastolic Doppler flow velocity (E) to tissue Doppler velocity (e') of the mitral annulus (E/e')
- Improved indices of diastolic function with an increase in the e' velocity (faster relaxation)
- Improvement in clinical status as measured by 6-min walk and MLWHFQ

Study design

This will be a **double-blinded placebo controlled study design**. Subjects will be randomized to the Chronic AT1 receptor blockade or to the placebo group. We will compare the effect of 12 weeks of Chronic AT1 receptor blockade with Candesartan (n=38) or placebo (n=38) on cardiorenal and humoral in subjects with compensated CHF and renal dysfunction

Specific methods

i) Study population

76 Subjects with compensated CHF with renal dysfunction

Inclusion Criteria:

- Left ventricular ejection fraction of equal or less than 40% assessed by echocardiography, nuclear scan, MRI or left ventriculogram within the past 48 months.
- Stable New York Heart Association (NYHA) class II and III symptoms as defined by: no change in NYHA symptoms over the past 3 months, on stable doses of ACE inhibitor, beta blocker, digoxin and furosemide over the last 4 weeks and no episode of decompensated CHF over the past 6 months.
- Calculated creatinine clearance of less than 90 ml/min and greater than 20 ml/min, using the MDRD formula assessed within the past 48 months and a confirmatory calculated creatinine clearance equal or less than 80 ml/min and greater than 20 ml/min at the time of enrollment.

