record it, along with heart rate and weight. They will also receive a weekly phone call to review status. During the study, if patient develops symptomatic hypotension as defined above or an increase of plasma creatinine of > 0.3 mg/dL or hyperkalemia > 5.7 meq/ml, the dose will be reduced by 50%. If those parameters persist, the dose will be decreased further by 50%. At the discretion of the investigator, the medication can be discontinued.

At the end of the twelve-week study period (± 7 days), subjects will be admitted to the CRU again. A 6-min walk, MLHFQ, echocardiography, renal clearance, humoral determination and renal functional reserve will be performed in the same manner as the baseline study. Subjects will also perform a 24-hour urine collection the day prior to their return visit for determination of sodium excretion, creatinine clearance and microalbuminuria. Subjects will be dismissed after the renal clearance study.

iii) Sample size and statistical analysis

The sample size calculation and statistical analysis have been designed in collaboration with the Division of Biostatistics, ([name] and [name]).

The **primary analysis** for this study will be a comparison of the parameters of interest between the AT1 receptor blockade group and placebo. This analysis will be completed using a two-sample t-test comparing the change from baseline to the latest time point available. In addition to this primary analysis, if complete or near complete data is available, a secondary analysis will be completed using all data from baseline to the latest available time point. The groups will be compared in this analysis using a 2 factor repeated measures analysis of variance. Values will be expressed as the mean \pm SE. A statistically significant difference will be considered to be present when $p<0.05$.

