Sample size calculation: Preliminary data were obtained from the applicant's previous study. These data were used to estimate the standard deviation of the change in each parameter in the treated group. It was assumed that the standard deviation in the untreated group would be only $\frac{1}{2}$ of that in the treated group, since the treated group is composed of responders and non-responders, while the untreated group response data is largely due to biological and measurement variability between 2 occasions, with little or no actual signal. In light of this argument, allocation will be unequal in order to optimize the precision of the group comparison. Specifically, there will be 2 treated subjects per 1 placebo subject. Preliminary data for this analysis is provided below.

	Change from Baseline in AT1 group	Change from Baseline in Placebo group	N
GFR ml/min	-20.67 ± 15.97	1.13 ± 12.18	6
Na excretion mEq/min	-11.89 ± 27.27	-10.78 ± 20.08	6
ANG II pg/ml	29.32 ± 107	11.98 ± 43.67	6
Renin ng/ml/hr	4.9 ± 6.5	3.9 ± 4.4	6

So based on this preliminary data, the study will have **90% power** to detect the following differences using 38 patients in the AT1 receptor blocker group, and 38 in the placebo group.

	Detectable change	N/group
GFR ml/min	15	38 and 38
Na excretion mEq/min	25.4	38 and 38
ANG II pg/ml	100	38 and 38
Renin ng/ml/hr	6.1	38 and 38

Data Handling

The study coordinator will enter data into a Microsoft Excel spreadsheet. In addition to cardiorenal and humoral data mentioned above, 6 min walk, MLWHFQ scores and clinical data including cardiovascular risk factors, medications, clinical events, laboratory data and physical exam will be collected. Data will be stored on a

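### The pilot placebo figures do not support the half-SD assumption behind 2:1 allocation, and the 90%-power table follows from neither SD set at 38 and 38

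*Combined protocol and SAP*

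**What the plan says.** Everything at issue is in section iii), Sample size and statistical analysis. The primary analysis is a "two-sample t-test comparing the change from baseline to the latest time point available". For the sample size, pilot data supply the SD of change in the treated group. The placebo SD is assumed: "It was assumed that the standard deviation in the untreated group would be only" half the treated value, on the argument that a treated group mixes responders and non-responders while a placebo group shows little beyond biological and measurement noise. The plan then concludes: "In light of this argument, allocation will be unequal in order to optimize the precision of the group comparison". It gives the ratio: "Specifically, there will be 2 treated subjects per 1 placebo subject".

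A table of pilot changes follows, with a ± value for both groups and a single N of 6. The plan next says that "the study will have 90% power to detect the following differences", namely GFR 15 ml/min, sodium excretion 25.4, angiotensin II 100 pg/ml and renin 6.1 ng/ml/hr. It describes the group sizes behind that claim as "using 38 patients in the AT1 receptor blocker group, and 38 in the placebo group". The Abstract and the Study design section also give equal groups: "Chronic AT1 receptor blockade with Candesartan (n=38) or placebo (n=38"). The Study population section gives 76 subjects in total.

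**The concern.** The allocation rule rests on one number, the placebo/treated SD ratio. The plan assumes that number although a placebo column from its own pilot work is printed a few lines below, and it does not say why that column was set aside. If the true ratio is nearer three quarters than one half, 2:1 loses its stated justification for GFR and sodium excretion, both named in Hypothesis 1.

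The power statement has a related problem. A reader cannot tell which SDs or group sizes produced the detectable differences, so the 90% figure cannot be relied on in either direction. Someone who noticed only that 2:1 clashes with 38 and 38 could resolve the clash by restoring 2:1 on this rationale.

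**Working it through.** **Inputs** (pilot table, change from baseline, AT1 group then placebo): GFR ± 15.97 and ± 12.18; sodium ± 27.27 and ± 20.08; angiotensin II ± 107 and ± 43.67; renin ± 6.5 and ± 4.4. Significance level 0.05, taken as two-sided because sidedness is not stated; power 90%; total 76. No dropout allowance is stated, so none is applied.

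**1. SD ratios.** 12.18/15.97 = 0.76; 20.08/27.27 = 0.74; 43.67/107 = 0.41; 4.4/6.5 = 0.68. These hold whether ± is SD or SE, provided that N is the same in both columns.

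**2. When 2:1 helps.** The variance of the difference is s1²/n1 + s2²/n2. At fixed total N it is smallest when n1/n2 = s1/s2, so a ratio of exactly one half does give 2:1. The printed ratios give 1.31:1 (GFR), 1.36:1 (sodium), 2.45:1 (angiotensin II) and 1.48:1 (renin). 2:1 beats 1:1 when 1.5·s1² + 3·s2² < 2·s1² + 2·s2², that is, when s2/s1 < √0.5 = 0.707. GFR and sodium lie above that limit.

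**3. Size of the effect.** The nearest whole split of 76 to 2:1 is 51:25. For GFR with the printed values:
- 38:38: (15.97² + 12.18²)/38 = 10.62
- 51:25: 15.97²/51 + 12.18²/25 = 10.93, a rise of 3.0%

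The same calculation gives +1.8% for sodium, -1.1% for renin and -14% for angiotensin II. Under the half-SD assumption it is -10% for every parameter. On the SE scale the two losses are √1.030 = 1.015 and √1.018 = 1.009, or about 1.5% and 0.9%.

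**4. The plan's detectable differences.** The approximate formula is (1.960 + 1.282) × √(s1²/n1 + s2²/n2). For GFR at 38:38 with half-SD it gives 3.242 × 2.896 = 9.4; the noncentral t with unequal variances gives 9.6. Noncentral t results at 38:38, with ± read as SD:

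| | Stated | Half-SD | Printed SDs | Power at stated difference, printed SDs |
|---|---|---|---|---|
| GFR | 15 | 9.6 | 10.7 | 99.5% |
| Sodium | 25.4 | 16.3 | 18.1 | 99.5% |
| Angiotensin II | 100 | 64.0 | 62.0 | >99.9% |
| Renin | 6.1 | 3.89 | 4.19 | 99.7% |

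Under half-SD, power at the stated differences is 99.9%. Neither SD set reproduces the table. A pooled-variance t changes little at 38:38 (GFR 9.5 under half-SD).

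**5. Where the figures may come from.** The stated differences are 0.93 to 0.94 of the treated SD (15/15.97 = 0.94; 25.4/27.27 = 0.93). Several settings come close:
- 38:19 with equal SDs, pooled t: 14.8, 25.3, 99.2, 6.03
- 25:25 with equal SDs: 14.9, 25.5, 100.1, 6.08
- 19:10 with half-SD: 15.0, 25.6, 100.3, 6.09

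The text does not say which, if any, was used.

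**6. If ± is SE.** The pilot ± is unlabelled, and the same section says that values will be expressed as mean ± SE. With n = 6 per group, SD = SE × √6; for GFR that is 15.97 × 2.449 = 39.1 and 12.18 × 2.449 = 29.8. Power at the stated differences, at 38:38 with the printed values, is then about 46% (GFR), 46% (sodium), 57% (angiotensin II) and 49% (renin). With half-SD it is about 54-55%.

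**The case against.** The plan presents half-SD as an assumption with a mechanistic reason, not as an estimate from the placebo column, and six patients cannot overturn it. Reading N as 6 per group and treating the columns as independent, the 95% F-interval for the GFR ratio is 0.763/√7.146 to 0.763 × √7.146, or 0.29 to 2.04. That includes one half (p = 0.38). Angiotensin II agrees with the assumption, and 2:1 would help there. This objection stands: the pilot does not support the premise for three parameters, but it does not disprove it.

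The precision loss is also small, and it arises only if 2:1 is carried out, whereas every stated group size is 38. That stands too.

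A reader might infer that the planning SE is too small and the trial underpowered. An SE built on half-SD would indeed be smaller than one from the printed GFR values (2.90 against 3.26 at 38:38). But the printed table does not reflect such an SE. A detectable GFR difference of 15 implies 15/3.242 = 4.63, about 42% larger than 3.26. With ± read as SD, the plan's own figures understate power. Under the SE reading power is low, but the cause is the unlabelled ±, not the half-SD premise.

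A reader might also infer that the pilot table settles the allocation in favour of 1:1. It does not. None of the four optima is 1:1, and two of the four parameters do better at 2:1.

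**Conclusion.** The half-SD assumption lacks support in the plan's own pilot data for GFR, sodium and renin, and on those data 2:1 does not optimise precision for the two renal outcomes. The direct cost of 2:1 would be minor: 3.0% and 1.8% in variance, set against gains of 1.1% for renin and 14% for angiotensin II.

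The larger consequence is that the section cannot be followed from assumption to result. Its allocation sentence conflicts with its group sizes, and its detectable differences come from neither SD set at those sizes. Actual power at the stated differences is above 99% or roughly one half, depending on what ± means. These results assume a two-sided test, N = 6 per group and no dropout. Neither underpowering nor a pilot-based case for 1:1 is established.

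**What to change.** Delete the sentence that sets 2 treated per 1 placebo, together with the claim that unequal allocation optimises precision. Keep 38:38, because every stated group size already uses it, and confirm that the randomisation schedule is 1:1. Drop the half-SD assumption or give evidence for it. Label the pilot ± as SD or SE and say whether N = 6 is per group. Recompute the detectable differences at 38 and 38 from both printed columns, stating the sidedness and the form of the t-test. If ± is SD, the 90%-power figures become about 10.7, 18.1, 62.0 and 4.19.

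The cost is wording and one table, with the total of 76 unchanged if ± proves to be SD. Keeping 38:38 gives up the 14% variance reduction that 2:1 might have brought for angiotensin II. If ± proves to be SE, the 90% claim at the stated differences cannot stand at 38 and 38, and the plan should say so.

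### The 90% power table does not belong to the 38 + 38 design, and the same paragraph still specifies 2:1 allocation

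*Combined protocol and SAP*

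**What the plan says.** All of this is in the combined protocol and SAP, mainly section iii) Sample size and statistical analysis.

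- **Test.** The primary analysis is a "two-sample t-test comparing the change from baseline to the latest time point available". The significance level is 0.05. Sidedness is not given, and neither a multiplicity adjustment nor a dropout allowance is stated.
- **Variance assumption.** "It was assumed that the standard deviation in the untreated group would be only" half of that in the treated group.
- **Allocation, first version.** Because of that assumption the paragraph makes allocation unequal: "Specifically, there will be 2 treated subjects per 1 placebo subject".
- **Allocation, second version.** The power sentence that follows claims power "to detect the following differences using 38 patients in the AT1 receptor blocker group, and 38 in the placebo group". Every row of the detectable-change table, the Abstract and the Study design section also give 38 and 38, and Study population gives 76 subjects.
- **Inputs.** A preliminary table with N = 6 gives mean ± an unlabelled figure for the change in each arm.
- **Output.** 90% power for changes of 15 (GFR, ml/min), 25.4 (sodium excretion, mEq/min), 100 (angiotensin II, pg/ml) and 6.1 (renin, ng/ml/hr).

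**The concern.** This calculation is the only justification given for 76 patients. It names two allocation ratios that exclude each other. Its argument for unequal arms, a smaller placebo SD, is then left unused by an equal-arm table. A reader therefore cannot tell which ratio, which placebo SD or which target difference the trial was planned on. The Study protocol section leaves the randomization schedule to the Division of Biostatistics without stating a ratio, so this text is where the ratio should be settled.

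The label on the ± matters as well. The paragraph says the preliminary data served to estimate standard deviations, but the preceding analysis paragraph says "Values will be expressed as the mean" with its SE. The two readings put the error in opposite directions.

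**Working it through.** **Inputs (Sample size calculation; ± read as SD)**

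| | Treated SD | Preliminary placebo SD | Placebo/treated | Printed detectable change | Printed change ÷ treated SD |
|---|---|---|---|---|---|
| GFR | 15.97 | 12.18 | 0.76 | 15 | 0.939 |
| Na excretion | 27.27 | 20.08 | 0.74 | 25.4 | 0.931 |
| ANG II | 107 | 43.67 | 0.41 | 100 | 0.935 |
| Renin | 6.5 | 4.4 | 0.68 | 6.1 | 0.938 |

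**Method.** Detectable difference = λ × SE, where SE = √(s₁²/n₁ + s₂²/n₂). λ is the noncentrality that gives 90% power for a two-sided t-test at 0.05 with n₁ + n₂ − 2 degrees of freedom. For 38 + 38 (74 df), λ = 3.284.

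**Step 1: try to reproduce the plan's figures at 38 + 38.** GFR in full:

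- Placebo SD half the treated SD (the plan's assumption): SE = √[(15.97² + 7.985²)/38] = 2.897; 3.284 × 2.897 = 9.51.
- Preliminary placebo SD: SE = √[(15.97² + 12.18²)/38] = 3.258; detectable 10.70.
- Treated SD in both arms (a conservative bound, not an assumption of the plan): SE = √[2 × 15.97²/38] = 3.664; detectable 12.03.

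All four rows:

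| | Printed | Half SD | Preliminary placebo SD | Treated SD in both arms |
|---|---|---|---|---|
| GFR | 15 | 9.51 | 10.70 | 12.03 |
| Na excretion | 25.4 | 16.24 | 18.04 | 20.55 |
| ANG II | 100 | 63.74 | 61.58 | 80.62 |
| Renin | 6.1 | 3.87 | 4.18 | 4.90 |
| Printed value too large by | | 56–58% | 40–62% | 24–25% |
| Power at printed values | | 99.9% | 99.5–99.95% | 98.0–98.1% |

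The 62% is angiotensin II: 100/61.58 = 1.62. No column returns the printed values.

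**Step 2: try the stated 2:1 ratio with the stated half-SD assumption.** 38 + 19 gives 10.47 / 17.88 / 70.15 / 4.26. Splitting 76 as 51 + 25 gives 9.03 / 15.41 / 60.47 / 3.67. Neither matches.

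**Step 3: try unstated settings.** A Bonferroni level of 0.0125 at 38 + 38 with the treated SD in both arms gives 14.15 / 24.16 / 94.78 / 5.76, still below the printed values. A one-sided test widens the gap.

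**Step 4: what does reproduce the table.** The printed change is a nearly constant 0.93–0.94 treated SDs in every row, while the placebo/treated ratio runs from 0.41 to 0.76. The preliminary placebo SDs were therefore not used. With the treated SD in both arms, two designs fit:

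- 38 + 19: 14.81 / 25.28 / 99.20 / 6.03 (power at the printed values 90.3–90.7%).
- 25 + 25: 14.94 / 25.52 / 100.13 / 6.08 (power 89.7–90.2%).

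Neither is 38 + 38, and neither uses the half-SD assumption.

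**Step 5: what 15 ml/min GFR would need.** 90% power takes 16 per arm (half SD), 20 (preliminary placebo SD) or 25 (treated SD in both arms). Arms of 38 could thus lose 58%, 47% or 34% of patients: 1 − 16/38, 1 − 20/38, 1 − 25/38.

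**Step 6: if ± is SE.** SD = SE × √6, so every SE and detectable difference in Step 1 is multiplied by 2.449. For GFR at 38 + 38 this gives 23.3, 26.2 and 29.5 ml/min. Power at the four printed values is 54–55% (half SD), 46–58% (preliminary placebo SD) or 37–38% (treated SD in both arms).

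**The case against.** The strongest reply is that the error is harmless. If ± is SD, the trial has more than the stated 90% power for the differences it names, and no patient number, test or decision rule changes. That stands, and it limits the weight of the point: the trial is misdescribed by this table, not underpowered by it.

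Second, the SE reading has less support. The sentence about SE most naturally describes how trial results will be reported, the sample-size text speaks of estimating the standard deviation, and the table can be rebuilt by entering the ± values as SDs. This makes SD the likelier reading. It shows how the planners used the figures, though, and cannot prove what the source table reported, so the label still has to be checked.

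Third, 38 and 38 is the dominant statement and the 2:1 text looks like a remnant. That is plausible, and nothing shows that the randomization schedule was affected. Only the sponsor can confirm it, and the current text contains both.

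Fourth, the half-SD assumption is itself optimistic. The preliminary placebo/treated ratios are 0.76, 0.74, 0.41 and 0.68, so three of the four exceed one half. That is a fair warning against relying on 9.5 ml/min for GFR alone, and the fix allows for it.

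Finally, the idea that the table was carried over from another design is an inference. Two designs fit about equally well, and the conclusion does not depend on it.

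**Conclusion.** The concern holds. The allocation contradiction is plain on the page and does not depend on any SD. The table is not the 90%-power result for 38 + 38 under any assumption the plan states, nor for 2:1 with the half-SD assumption. With ± as SD, the printed changes are too large by 56–58% on the plan's own assumption, by 40–62% with the preliminary placebo SDs, and by 24–25% even with the treated SD in both arms. True power at the printed changes is 98.0–99.95%. With ± as SE, the table is wrong in the other direction, with power of about 37–58%.

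This rests on a two-sided 0.05 level, which the plan does not spell out, and on complete data in all 76 patients. The SDs come from N = 6. If that is per group, the 95% interval for the GFR SD of 15.97 is about 10.0 to 39.2, so every restated value is a planning figure only. The point should be fixed; on the SD reading it does not threaten the trial's power for its stated targets.

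**What to change.** 1. State one allocation. Keep 38 + 38, and remove or reconcile the 2:1 text and its rationale. Confirm that the randomization schedule agrees.
2. Check the source of the preliminary table and label the ± as SD or SE. Say whether N = 6 is per group.
3. Name the placebo-SD assumption and the sidedness of the test.
4. Restate the table. If ± is SD, suitable text is: With 38 patients per arm and a two-sided two-sample t-test at 0.05, the study has 90% power to detect differences of 12.0 ml/min (GFR), 20.6 mEq/min (Na excretion), 80.6 pg/ml (ANG II) and 4.9 ng/ml/hr (renin) if the SDs are equal, and 9.5, 16.2, 63.7 and 3.9 if the placebo SD is half the treated SD. Give both sets, because the preliminary data do not support the half-SD assumption in three of the four rows.
5. Alternatively, keep the printed differences, state power of about 98–99.9%, and note that 16–25 evaluable patients per arm would give 90% power for 15 ml/min GFR, the remainder being allowance for loss.

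The cost is one paragraph and one table, with no extra patients if ± is SD. If it proves to be SE, the target differences or the sample size must be reconsidered, because 38 + 38 would then detect only 23.3–29.5 ml/min for GFR.

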After an equilibration period of 45 minutes, urine and blood samples are collected at 30-minute intervals for 3 periods to determine the baseline GFR and urinary sodium excretion (UNaV). Blood pressure will be measured at 20-minute intervals by using automatic blood pressure cuff, and heart rate will be continuously monitored. Urinary samples for determination of volume, sodium, potassium, lothalamate, and PAH, will be obtained at the end of each clearance period. Venous blood samples for lothalamate, PAH and sodium will be obtained at the middle of each clearance period. During the first clearance, venous blood samples for renin, aldosterone, angiotensin II, ACE, ACE 2, angiotensin 1-7, ANP, BNP, Bradykinin, NO, DNA, protein and cGMP will be obtained and urine samples for cGMP will also be obtained. BUN will also be run. Echocardiography will be performed after these baseline clearances as described.

At the completion of the baseline assessments, subjects will be randomized to Candesartan or placebo group. The randomization schedule will be provided by the Division of Biostatistics, implemented by the Mayo Pharmacy and administered by the CRU staff. The investigators and the CRU staff will not be aware of the randomization arm the subject is assigned to.

Subjects will receive the first dose of study drug in the CRU. Subjects will be started at 4 mg once a day. Thereafter, both blood pressure and heart rate (by electrocardiography) will continue to be monitored for the next 4 hours. If the patients develop symptomatic hypotension as defined by systolic blood pressure of ≤ 85 mmHg, with lightheadedness, dizziness or visual symptoms after the first dose of the medication in the CRU, the patient will be excluded from the rest of the study. The dose will be doubled every 14-18 days as tolerated to a goal of 16 mg a day or highest dose tolerated. Patients will get blood draw 7-10 days after each dose increase to measure plasma creatinine and potassium until target dose is achieved. *If there should be a potassium result <3.5 or >6.0 , subjects will need to have labs redrawn the same day.* Thereafter, subjects will get blood draws every 4 weeks (± 3 days). If distance indicates, blood draws will be arranged at the participants local clinic. Subjects will also have access to a 24-hour phone number should they have any questions or develop any side effects. They will be instructed to measure their blood pressure weekly and

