- Patients will have blood drawn to measure plasma creatinine and potassium 7-10 days after every dose increase until target dose is achieved. Thereafter, subjects will get blood draws every 4 weeks. *If there should be a potassium result <3.5 or >6.0, subjects will need to have labs redrawn the same day.*
- Subjects will also have access to a 24-hour phone number should they have any questions or develop any side effects.
- They will be instructed to measure their blood pressure weekly and record it, along with heart rate and weight.
- They will also receive a weekly phone call to review status.
- During the study, if patient develops symptomatic hypotension as defined above or an increased of plasma creatinine of > 0.3 mg/dL or hyperkalemia > 5.7 meq/ml, the dose will be reduced by 50%. If those parameters persist, the dose will be decreased further by 50%. At the discretion of the investigator, the medication can be discontinued

The following stopping rule will be applied to ensure patient safety

If the patients develop symptomatic hypotension as defined by systolic blood pressure of < 85 mmHg, with lightheadedness, dizziness or visual symptoms after the first dose of the medication in the CRU, the patient will be excluded from the rest of the study. During the study, if patient develops symptomatic hypotension as defined above or an increase in plasma creatinine of > 0.3 mg/dL or hyperkalemia > 5.7 meq/ml, the dose will be reduced by 50%. If those parameters persist, the dose will be decreased further by 50%. If those parameters persist, the subject will be withdrawn from the study

Other potential minor risk includes:

The risks of blood drawing include bleeding at the puncture site, bruising and pain. These risks occur in a very small portion of the population. We will exclude patients with hemoglobin of < 9 g/dL. The blood draw amount for this study is 200 mLs.

This protocol may be hazardous to an unborn child. There is no medical information to determine whether there are significant risks to a fetus carried by a mother who is participating in this study. Therefore, female

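### The stopping rule takes randomised subjects out of the study, and with them presumably their only follow-up GFR; any bias is probably small and its direction is not known

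*Combined protocol and SAP*

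**What the plan says.** Randomisation comes before the first dose (ii, Study protocol): "At the completion of the baseline assessments, subjects will be randomized to Candesartan or placebo group". Every later removal is therefore a post-randomisation loss.

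The protocol describes the dose-reduction pathway three times, with the same triggers and the same two 50% cuts:

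- Study protocol section: "At the discretion of the investigator, the medication can be discontinued".
- A protective-measures bullet under Potential risks and Protection against risk ends the same way.
- The stopping rule that follows those bullets: "If those parameters persist, the subject will be withdrawn from the study".

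For symptomatic hypotension after the first dose, "the patient will be excluded from the rest of the study".

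Clearance GFR is measured at baseline and at the twelve-week admission, where "renal clearance, humoral determination and renal functional reserve will be performed in the same manner as the baseline study". The safety draws in between measure only creatinine and potassium. The primary analysis (iii, Sample size and statistical analysis) is a two-sample t-test "comparing the change from baseline to the latest time point available". The plan gives no missing-data method, no analysis set and no visit for withdrawn subjects.

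**The concern.** One trigger, rising creatinine, is itself a marker of the GFR outcome. The risk section names all three triggers as the main worry when candesartan is added to an ACE inhibitor. Losses could therefore be more frequent on candesartan and fall on subjects whose GFR is doing worse.

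The primary-analysis wording does not settle how such a subject is handled, because GFR has no post-baseline value before week 12. The subject either leaves the analysis or, if baseline counts as the last available value, contributes a change of zero. The two choices can push the estimate in different directions. The inconsistent texts also leave it to local judgement whether a subject loses drug only or leaves the study.

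**Working it through.** The plan gives no figure for loss, so there is none to reproduce. The check asks how large the bias could be and whether the rule can act before week 12.

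**Inputs from the documents.** The GFR change table under Sample size gives 15.97 (AT1 blockade) and 12.18 (placebo), from n = 6. The ± values are unlabelled and are taken as SDs; every bias below scales with them. There are 38 subjects per arm.

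**Assumed inputs.** Loss p on candesartan/placebo is 5%/2% (about 2 and 1 of 38), or 10%/3% (about 4 and 1) as a heavier case. The correlation r between the withdrawal trigger and GFR change is 0.3 to 0.5.

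**Model.** The lowest share p of each arm on a normal index correlated r with GFR change is withdrawn; f is the normal density at the p quantile and μ the arm's true mean change.

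- Dropped: arm mean = μ + SD·r·f/(1−p)
- Counted as zero: arm mean = μ(1−p) + SD·r·f

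For 5% and 2%, f = 0.1031 and 0.0484. With no true effect and r = 0.3:

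- Dropped: 15.97×0.3×0.1031/0.95 − 12.18×0.3×0.0484/0.98 = 0.52 − 0.18 = **+0.34 ml/min**
- Counted as zero: 15.97×0.3×0.1031 − 12.18×0.3×0.0484 = 0.49 − 0.18 = **+0.32 ml/min**

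| No true effect, r = 0.3 to 0.5 | Dropped | Counted as zero |
|---|---|---|
| 5%/2% | +0.34 to +0.57 | +0.32 to +0.53 |
| 10%/3% | +0.68 to +1.13 | +0.59 to +0.99 |

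Simulated type I error (100,000 trials, pooled t-test, two-sided 0.05), with subjects dropped, is about 5.2 to 5.5% at 5%/2% and 5.7 to 6.6% at 10%/3%, against about 5% with no loss. At 10%/3% and r = 0 it is already about 5.2%, from unequal SDs combined with unequal numbers, so not all of the excess is bias. With equal loss and equal SDs the bias is zero.

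**Direction.** Take a true gain of 15 ml/min, the plan's detectable difference, placebo change 0 and 5%/2%. Dropping gives 15 + 0.34 to 15 + 0.57, about 15.3 to 15.6. Counting as zero gives 15×0.95 + 0.32 to 15×0.95 + 0.53, about 14.6 to 14.8, which leans against candesartan. The zero-change lean reverses once the true gain passes 0.317/0.05 = 6.3 ml/min (r = 0.3) or 0.529/0.05 = 10.6 ml/min (r = 0.5).

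**Recovery off drug.** The values above treat the on-drug change as the truth. For the effect of assignment, if a withdrawn subject's change reverses fully by week 12, the bias at 10%/3%, dropped, shrinks to 0.68 − 0.59 = 0.09 up to 1.13 − 0.99 = 0.14.

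**Timing of creatinine withdrawals.** The dose reaches 8 mg at day 14–18 and 16 mg at day 28–36. A draw follows 7–10 days after each increase; once the target dose is reached, "Thereafter, subjects will get blood draws every 4 weeks" (±3 days in the study protocol section). Withdrawal needs three abnormal results: the trigger, then one after each halving. Two 4-weekly intervals add 2×25 = 50 to 2×31 = 62 days.

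- From 8 mg: day 14+7+50 = 71 to day 18+10+62 = 90
- From 16 mg: day 28+7+50 = 85 to day 36+10+62 = 108
- Week-12 window: 84 ± 7, day 77 to 91

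The third abnormal result therefore falls near or after the week-12 visit in most cases. Hypotension can act sooner: "They will also receive a weekly phone call to review status", so three weekly findings span 14 days, but its link with GFR is weaker.

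**The case against.** The strongest reply is that there is no true contradiction. An investigator may stop the drug at any point, and must withdraw the subject if the trigger outlasts the second halving; both can be followed. This stands: the texts are inconsistent but reconcilable. It does not help the analysis, because under that reading the mandatory step is still withdrawal from the study.

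Second, the missing week-12 GFR is inferred. No section says that withdrawn subjects skip the visit. That is correct, but none provides for their attendance either.

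Third, two dose halvings should resolve many drug-caused triggers, so the cases that persist may be spread more evenly over the arms than the assumed losses. The risk section also calls the overall risk small. With the timing result, this makes the 10%/3% case hard to defend as a central value. It does not remove the concern: no recheck interval after a dose cut is specified, and earlier rechecks would bring withdrawals forward.

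A reader might infer that the trial is biased in favour of candesartan, pointing to the preliminary GFR change of −20.67 on AT1 blockade against +1.13 on placebo. The documents do not support that. Those data come from six subjects in a study that is not described, and the acute losartan crossover under Preliminary Studies found no GFR reduction when losartan accompanied furosemide. No loss rate is given, and the direction depends on the true effect and on how withdrawn subjects are counted.

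Last, the stated aim is the effect of twelve weeks of AT1 blockade, which can be read as an on-drug question. A supportive on-drug analysis answers that.

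**Conclusion.** The point holds as a minor design flaw. Followed as written, the stopping rule removes randomised subjects on criteria that include a correlate of GFR. It presumably leaves them without the single follow-up GFR, and the plan does not say how they are then counted. If such losses differ by arm and relate to GFR, the comparison can be biased.

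Size and direction are unknown, and the effect is probably small: about +0.3 to +0.6 ml/min with no true effect if subjects are dropped, resting wholly on the assumed 5%/2% loss and r = 0.3 to 0.5. That compares with a stated detectable difference of 15 ml/min. Most creatinine-triggered withdrawals would come too late to cost a week-12 value. The claim is limited to GFR, and no GFR bias is claimed for first-dose hypotension.

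**What to change.** 1. In the study protocol section, the risk-section bullet and the stopping rule, state one rule: if a trigger persists after two halvings, study drug is permanently stopped and the subject stays in the study. Apply the same rule after first-dose symptomatic hypotension, so that all randomised subjects are kept.
2. Ask every randomised subject to attend the already planned week-12 clearance visit, if the investigator judges it safe.
3. Replace the latest-available-value wording for GFR with change to week 12 by assigned arm, and add an on-drug analysis as supportive.
4. Report missing week-12 GFR by arm and reason.

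The cost is mainly wording, and drug is still stopped for safety. The downsides are that some week-12 values will be off drug, so the main estimate becomes the effect of assignment, and that a few stopped subjects undergo the clearance visit with its fasting, water loading and iothalamate infusion.
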